Our long-term goal is to develop a biomarker of treatment in patients receiving ECT. By having this biomarker, practitioners could move towards individualized treatment parameters. We hypothesize that ictal power and post-ictal infra-slow waves will be associated with clinical response and the choice of anesthetic agent will accentuate ictal or post-ictal morphology. We propose a pilot project using dcEEG to look at infra-slow waves in depressed patients receiving ECT randomized to ketamine or methohexitol. The rationale for this project is to identify biomarkers of treatment adequacy in ECT, which could lead to decreased morbidity and mortality with the procedure and lessen the burden of depression in our patient population.

Aim 1: Identify EEG biomarkers related to clinical response

PROTOCOL TITLE:

Hypothesis 1.1: Ketamine will be associated with increased ictal power and increased post-ictal suppression compared to methohexital

Hypothesis 1.2: Methohexital will be associated with post-ictal infra-slow waves

Hypothesis 1.3: Increased ictal power and infra-slow waves will be associated with clinical outcomes

At the completion of this pilot project, we expect to identify infra-slow characteristics using dcEEG that correspond with clinically effective treatment. We plan to further evaluate these phenomena as a potential biomarker of treatment adequacy with the goal of individualizing ECT treatments and improving standard of care.

2. Background

[figure not shown]
Historically it was thought that inducing a seizure was all that was needed to produce the clinical effects seen in ECT, but multiple studies across the past 8 decades have shown varying rates of efficacy and severity of side effects based on ECT stimulus parameters. We learned empirically that electrode placement (bitemporal versus unilateral) and stimulus parameters that affect electrical pulse and pulse train matter [10]. However, practitioners continue to focus on total charge as the primary metric, largely ignoring the role individual stimulus parameters play in the equation.

A biomarker of treatment response would help in evaluating clinical efficacy and accelerate evaluation of individual ECT parameters. There have been many potential biomarker for depression including hormones, cytokines, and neuro-imaging. These investigations have

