been met with disappointing results [11]. EEG has also been evaluated as a potential biomarker in ECT, and there have been several advances that warrant a revisit to this line of inquiry. Firstly, traditional EEG filters out low frequency bands. Our preliminary data shows large infra-wave phenomena suggesting significant inhibitory activity (see figure 1) using dcEEG. This newly-captured neuronal activity during ECT could act by itself or in conjunction with ictal and postictal phenomena observed in normally observed frequency bands as a potential biomarker of treatment adequacy. Secondly, the EEG we propose is 24-lead, whereas prior investigations used up to 19-lead [12-14]. Our group has noticed more pronounced infra-slow waves in a subsection of the leads, meaning with greater resolution, we may be picking up neuronal activity that was previously missed. Thirdly, the studies evaluating EEG were carried out before ECT parameters were optimized with respect to seizure efficiency (high frequency and short pulse train duration). Current ECT devices have improved parameter ranges to individualize and optimize clinical outcomes.

3. Study Design

Figure 1: 24-Lead ECT capturing spreading depression (box with arrow)

PROTOCOL TITLE:

This single-site clinical investigation will use assessments before, during and after the ECT series. At the first time point (T1), subjects will be randomized to ketamine or methohexitol induction. The second time point (T2) will be the second ECT treatment. The third time point (T3) will occur midpoint, and the final time point (T4) will be the endpoint at the last ECT treatment. The patient will be blinded to the anesthetic.

4. Inclusion and Exclusion Criteria

Inclusion Criteria, Major Depressive Disorder (MDD) & Bipolar Disorder (BPD)-Depressed: 1) Structured Clinical Interview for DSM-5 will confirm diagnosis of MDD or BPD-depressed (with or without psychotic features); 2) the clinical indications for ECT including treatment resistance or a need for a rapid and definitive response; 3) Hamilton Depression Rating Scale 24-item (**HDRS-24**) ≥ 21 ; and 4) age range between 18 and 65 years of age. Per UNM ECT clinical service recommendations, subjects will be requested to taper and dc scheduled psychotropic medications with the exception of as needed medications for sleep or anxiety.

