Exclusion Criteria: 1) Defined neurological or neurodegenerative disorder (e.g., history of head injury with loss of consciousness > 5 minutes, epilepsy, Alzheimer's disease); 2) other psychiatric conditions (e.g., schizophrenia, schizoaffective disorder, bipolar disorder); and 3) current drug or alcohol use disorder, except for nicotine and marijuana 4) adults unable to consent, pregnant women, prisoner; 5) Have contraindications to methohexitol and ketamine as described in the package inserts; 6) non-English speakers; 7) Patients that cannot tolerate Methohexitol and Ketamine.

5. Number of Subjects

26 subjects meeting the inclusion criteria will be recruited for this investigation. Our total sample size ($n = 26$) allows for a conservative 15% attrition rate leaving a final sample size of 22. This recruitment rate of 26 subjects per year will complete subject recruitment 1 year after study initiation. Sample size calculation is based on the 2004 Perera et al. paper examining ictal power between a threshold group and suprathreshold group (Cohen's $d = 1.19$) with variances of .24 and .25 respectively. Assuming a power of .8 and a two-sided alpha (.05), we will need 11 patients in each group to adequately power our analysis, which is in line with our recruitment projections.

6. Study Timelines

Individual subjects will have 4 points (T1-T4) in the study with the endpoint being their last treatment. ECT is done three times weekly and a typical series includes 8-12 treatments. This means that patients will be enrolled and participating in research for approximately one month. The study period will be one year long with an additional three months for analysis for a total of 15 months.

7. Study Endpoints

The primary endpoints include change in depression rating scale. Changes in depression rating will be compared with total ictal power and postictal suppression along with presence and power of infra-slow waves on dcEEG.

8. Research Setting

Patients will be recruited through the UNMH ECT consult service. All data collection will take place at the UNM Center for Psychiatric Research, or the ECT service at the University of New Mexico. All clinical assessments and neuropsychological testing will be conducted in an interview room or in a private patient room.

9. Resources Available

PROTOCOL TITLE:

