Investigators: The PI ([name]) is a board-certified Psychiatrist and Assistant Professor at UNM. He has been on the neuromodulation service and doing ECT for two years. He has a recent publication on electrode placement and ECT. He has .5 FTE devoted to completing this project as this constitutes his Master's Thesis in the MSCR program. He plans to apply to the CTSC for pilot grant funding.

10. Prior Approvals

Departmental Review Form signed by Department Chair uploaded into Click under "supporting documents."

11. Multi-Site Research

NA

12. Study Procedures

Clinical Assessments: The primary clinical response measure will be change in the QIDS C and QIDS SR [15]. The trained clinical rater will use the structured interview for the HDRS-24 to examine inter-rater reliability [16]. The initial visit will also include the Maudsley Staging Method Form for treatment resistance [17], ECT Appropriateness Scale to assess the indication for ECT [18], Medical History form to gauge overall medical burden, and Edinburgh Handedness Inventory [19].

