Study Protocol: Subjects will receive their baseline depression and cognitive assessment 0 to 48 hours prior to the first ECT session (T1). One day after the sixth ECT treatment (T3), subjects will receive their second depression and cognitive assessment. Treatments will continue thrice weekly until clinical response, which

PROTOCOL TITLE:

typically occurs between six and twelve treatments. The final assessment will occur after their last ECT treatment in the series (T4) and will include depression and cognitive assessments. DcEEG data will be collected at T1-T4 using a non-invasive cap that covers the patient's head. Per standard of care, change of electrode placement will be assessed at the midpoint (T2) by the treating psychiatrist. If the patient is not responding to ECT they may be switched from RUL to bitemporal placement. This assessment will not be affected by the research protocol.

13. Data Analysis

See effect size calculation in question #5 for hypothesis 1.1. To the best of our knowledge, spreading depression has never been studied in ECT (aside from our preliminary findings). We will use the effect size for hypothesis 1.1 to guide us. In terms of analyzing the mean power of the waves noted, we plan to calculate the sum of the mean power per epoch across T1-T4 data points to get total ictal power, as well as smaller epochs to calculate total infra-wave power and post-infra-wave suppression. We will also use chisq to compare number of infra-slow waves and t-tests to compare power of infra-slow waves and total ictal power of seizures and post-ictal suppression in the methohexitol group. We do not expect to see infra-slow waves in the ketamine group.

14. Provisions to Monitor the Data to Ensure the Safety of Subjects

Methohexitol and ketamine are both standard of care anesthetic agents used in ECT and the dcEEG device is worn on the scalp and is non-invasive. If the patient does not tolerate the anesthetic chosen, then they will be switched to the other anesthetic and act as a cross-over cohort. The medications and ECT device used in this study are standard of care. In the unlikely event that at the midpoint assessment (6 months) greater than 50% of patients have refused to wear the EEG cap, our study will not be sufficiently powered and will be terminated.

15. Withdrawal of Subjects

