Mecta 5000q: FDA approved for ECT with 2-channel FP1 FP2 EEG capabilities for clinical decision making

SMARTING EEG

32. Principal Investigator's Assurance

By submitting this study in the Click IRB system, the principal investigator of this study confirms that:

- The information supplied in this form and attachments are complete and correct.
- The PI has read the Investigator's Manual and will conduct this research in accordance with these requirements.
- Data will be collected, maintained and archived or destroyed per HSC Data Security Best Practices, including:
 1. **Best Practice for data collection** is for it to be directly entered onto a data collection form that is in a secured access folder on an HS drive behind a firewall, or in a secure UNM Data Security approved system such as RedCap.
 2. **Data collection of de-identified data**, if done in a clinical setting or other setting that does not allow direct entry into a secured system, may be done temporarily using a personal or university owned electronic storage device or hard copy document. **The important security safeguard is that no identifiers be include if the data is entered or stored using an untrusted device or storage.**
 3. **Permanent (during data analysis, after study closure)** storage must reside on HSC central IT managed storage. Processing of data (aggregation, etc.) are to be carried out in such a way as to avoid creating/retaining files on untrusted storage devices/computers. Trusted devices are HSC managed and provide one or more of following safeguards: access logs, encryption keys, backups, business continuity and disaster recovery capabilities.

PROTOCOL TITLE:

4. **Alternate storage media** must be approve by HSC IT Security as meeting or exceeding HSC central IT provided security safeguards.

Checklist Section

This section contains checklists to provide information on a variety of topics that require special determinations by the IRB. Please complete all checklists relevant to your research.

I. Waivers or Alterations of Consent, Assent, and HIPAA Authorization

Partial Waiver of HIPAA Authorization for Screening/Recruitment

Complete the following additional questions/attestations if the records you will review to identify potential subjects and/or determine eligibility include Protected Health Information (PHI).

1. Will you be recording any PHI when conducting the records review to identify potential subjects and/or determine eligibility?

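### Only the patient is masked: nothing masks the depression rater or cognitive tester to agent or dcEEG, which leaves the infra-slow-wave half of Hypothesis 1.3 open to expectation bias

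*Combined protocol and SAP*

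**What the plan says.** Section 3 (Study Design) randomizes patients to ketamine or methohexital and states: "The patient will be blinded to the anesthetic". No other section mentions masking of anyone.

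Section 12 (Clinical Assessments) states: "The primary clinical response measure will be change in the QIDS C and QIDS SR". QIDS-C is the clinician-rated form and QIDS-SR the self-report. The plan does not rank them or say who scores QIDS-C. A rater is mentioned only for the Hamilton scale: "The trained clinical rater will use the structured interview for the HDRS-24 to examine inter-rater reliability". Whether that rater works apart from the ECT team is not stated. The person who gives the cognitive battery is not identified either.

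Section 7 (Study Endpoints) ties the depression ratings to the EEG: "Changes in depression rating will be compared with total ictal power and postictal suppression along with presence and power of infra-slow waves on dcEEG". Hypothesis 1.3 in Section 1 reads: "Increased ictal power and infra-slow waves will be associated with clinical outcomes". Hypothesis 1.1 expects higher ictal power with ketamine, Hypothesis 1.2 expects infra-slow waves with methohexital, and Section 13 expects no such waves with ketamine.

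Sections 26 and 27 (as numbered in the body: Study Test Results, and Sharing Study Progress or Results) return depression, cognitive and dcEEG results to patients, without saying when.

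**The concern.** The outcome side of Hypothesis 1.3 rests partly on a clinician's judgement. The plan records in advance which patients are expected to show the candidate marker and that the marker is expected to go with benefit. A rater who knows the agent, or has seen the session's dcEEG, therefore knows who is supposed to improve. Even a small lean in scoring would appear as an association between infra-slow waves and outcome, which is the result the study is looking for.

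Randomization gives no protection, because the bias enters when the outcome is measured. No later analysis can separate it from a true association. The self-report form is a partial safeguard, since the patient is masked to agent, but dcEEG results returned before the last rating could weaken that too.

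**Working it through.** **1. Who is masked.** Sections 3, 12, 13 and 14 and the data-handling sections contain one masking statement, in Section 3, and it covers the patient only. The documents are silent on the rater and the tester.

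**2. Which way the bias would run.** Setting the hypotheses side by side:

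| EEG feature | Expected higher or present under | Hypothesis 1.3 expects it to go with | Effect of a rater who favours methohexital |
|---|---|---|---|
| Infra-slow waves | methohexital (H1.2; Section 13) | better outcome | pushes toward H1.3 |
| Ictal power | ketamine (H1.1) | better outcome | pushes against H1.3 |

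Knowing the agent points one way only for infra-slow waves. For ictal power it has no clear direction, so the calculation below is confined to infra-slow waves.

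**3. Inputs for the size.** The plan has no figure for rater bias to reproduce. The only plan input is the final sample in Section 5: 26 × (1 − 0.15) = 22.1, taken as 22, or 11 per group. The rest are assumptions:
- 8 of the 22 patients show waves;
- the rater shifts QIDS-C change in those patients by b = 0.2, 0.4 or 0.6 SD;
- there is no true association;
- the test is a two-sided 5% two-sample t-test with 20 degrees of freedom (critical value 2.086).

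**4. QIDS-C alone.** Noncentrality = b / √(1/n₁ + 1/n₂), and the false-positive rate is P(|T| > 2.086) under the noncentral t.
- 8 v 14: √(1/8 + 1/14) = 0.443. Noncentrality is 0.451, 0.903 and 1.354, and the rate is 0.071, 0.138 and 0.252. A simulation of 40,000 trials gives 0.072, 0.135 and 0.251.
- 11 v 11 (the shift follows the arm): √(2/11) = 0.426. Noncentrality is 0.469, 0.938 and 1.407, and the rate is 0.073, 0.145 and 0.268.

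**5. QIDS-C averaged with an unbiased QIDS-SR.** Assume equal SDs and correlation 0.7. The mean of the two shifts by b/2 and has SD √((1 + 0.7)/2) = 0.922, so the standardized shift is b/(2 × 0.922): 0.108, 0.217 and 0.325. For 8 v 14 the rate is 0.056, 0.075 and 0.108. Correlations from 0.5 to 0.9, in either split, give about 6%, 7–8% and 10–12%.

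**6. Which case applies.** The plan does not say. Section 12 names both forms without a rule for combining them, and Section 13 specifies no outcome test for Hypothesis 1.3.

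**The case against.** The other side has several fair points.

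- **Silence is not a statement that raters are unmasked.** This stands, and it is why the point is only that the rater may know.
- **Some separation already exists.** Section 8 places assessments in an interview or private room, Section 12 puts the T3 rating a day after treatment, and Section 16 sends recordings to a dedicated off-network device. Total ictal power sums over T1–T4, so it cannot be known before T4. This weakens the dcEEG route, especially for power. It does not mask the rater to agent, and agent alone is expected to predict the waves.
- **QIDS-SR comes from a masked patient.** This stands as a partial safeguard and roughly halves the standardized shift, as shown in step 5 of the working.
- **This is a small pilot sized on Hypothesis 1.1.** Hypotheses 1.1 and 1.2 have EEG outcomes, so biased depression ratings do not touch them.

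Three stronger readings are tempting, and the documents do not support them.

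- A reader might infer that an unmasked treating psychiatrist decides when treatment ends and so sets T4. Section 12 says "Treatments will continue thrice weekly until clinical response" but names no assessor. The treating psychiatrist is named only for the electrode-placement decision, which the plan says the research protocol does not affect.
- A reader might infer that knowing the agent biases all of Hypothesis 1.3. The table in the working shows that it has a clear direction only for infra-slow waves.
- A reader might infer that the research dcEEG can safely be kept from the treating psychiatrist because the ECT device is listed as "FDA approved for ECT with 2-channel FP1 FP2 EEG capabilities for clinical decision making". That one device entry does not establish what clinicians need for care.

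**Conclusion.** The gap is real and should be fixed. As written, the plan allows the clinician-rated half of its primary clinical measure to be scored by someone who knows the agent or the dcEEG, in a study whose stated expectations link agent, infra-slow waves and benefit. The consequence is confined to the outcome side of Hypothesis 1.3 for infra-slow waves, with the same lack of masking for the cognitive tests.

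On the assumptions stated (8 of 22 patients with waves, shifts of 0.2, 0.4 and 0.6 SD, no true association), the nominal 5% rate becomes about 7%, 14% and 25% on QIDS-C alone. It becomes about 6%, 8% and 11% if QIDS-C is averaged with an unbiased QIDS-SR at correlation 0.7. The higher figures should not be read as the error rate of the primary endpoint as a whole. The shifts, the split, the correlation and the test are all assumptions. Severity: should fix, and before enrolment, because ratings made without masking cannot be repaired afterwards.

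**What to change.** In Sections 3 and 12, state that:
- the existing trained clinical rater scores both QIDS-C and HDRS-24;
- this rater and the cognitive tester do not attend ECT sessions and are masked to arm and to dcEEG;
- baseline ratings are completed before the allocation is opened;
- dcEEG recordings stay on the dedicated device, unavailable to raters, until that patient's T4 ratings are locked.

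In Sections 26 and 27, state that dcEEG results are shared with patients only after that lock, so that QIDS-SR keeps its protection.

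Make no change to what the treating psychiatrist may see or to when treatment ends. Note only that Section 12 does not say who judges clinical response.

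The cost is protocol wording, a small scheduling constraint on which staff attend sessions, and a short delay in returning dcEEG results. No planned sample size changes. The documents do not say whether the trained rater and the tester currently have session duties, so the sponsor should confirm that they can be kept out.

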Neuropsychological Assessments: The Montreal Cognitive Assessment, a measure of global cognitive function that is sensitive to gross neurocognitive abnormalities, will be used for screening for preexisting cognitive impairment [20, 21]. The Dot Counting Test will measure effort. The Test of Premorbid Function estimates premorbid intellectual function [22] that will be used as a potential covariate in analyses. The Autobiographical Memory Test will assess free recall and retrieval patterns (specific versus general) of retrospective autobiographical memories [23-25]. The Hopkins Verbal Learning Test-Revised (HVLT-R) will measure learning strategies, free recall, and recognition memory [26]. The Delis Kaplan Executive Function System (DKEFS) Color-Word Interference and Verbal Fluency Test measures processing speed, sequencing and cognitive flexibility [27-31]. To minimize practice effects, we will use three different published versions of the HVLT-R at each time point [32]. Also, we will construct a reliable change index for all cognitive variables of interest [33]. Following published guidelines, we will compute the HVLT-R percent retention score, which will be our primary outcome measure [34]. The percent retention score is a useful measure of hippocampal dependent memory function that reduces the possibility of over-estimating memory function from immediate and delayed free recall scores [34]. The entire neuropsychological battery (completion time < 60 minutes) will be used to compute composite z-scores that represent global cognitive function at each time point for secondary analysis.

ECT: The treating anesthesiologist will determine the appropriate dose for this procedure. The anesthetic agents include methohexitol and ketamine, general anesthetics, and succinylcholine, a depolarizing neuromuscular blocker. Subjects will be randomized into methohexitol and ketamine arms prior to the first ECT treatment. Both induction agents are considered standard of care during ECT. The first ECT session will determine individual seizure thresholds to ensure subsequent treatments are delivered at supra-threshold intensities. Motor, electroencephalographic and heart rate parameters will be recorded for each treatment.

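### Section 5's claim of 80% power for ketamine v methohexital rests on an unjustified proxy effect (d = 1.19 from a stimulus-dose contrast), and even at that effect the planned t-test has about 76% power

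*Combined protocol and SAP*

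**What the plan says.** Section 5 (Number of Subjects) takes its effect size from a 2004 paper "examining ictal power between a threshold group and suprathreshold group", with a standardized difference of 1.19. At 80% power and two-sided alpha 0.05 it concludes that "we will need 11 patients in each group to adequately power our analysis". It recruits 26, which "allows for a conservative 15% attrition rate leaving a final sample size of 22".

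Section 13 (Data Analysis) assigns this calculation to Hypothesis 1.1. Section 1 (Objectives) defines that hypothesis as greater ictal power and post-ictal suppression with ketamine than with methohexital. Section 13 names t-tests for ictal power. For spreading depression, which it describes as unstudied in ECT apart from the group's preliminary findings, it says: "We will use the effect size for hypothesis 1.1 to guide us". It plans a chi-square test on infra-slow waves and t-tests on their power, and expects no such waves on ketamine.

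Section 3 (Study Design) gives the randomized contrast: "subjects will be randomized to ketamine or methohexitol induction". Section 12 (Study Procedures) says that the first session finds each patient's seizure threshold, "to ensure subsequent treatments are delivered at supra-threshold intensities". This applies to both arms.

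**The concern.** An effect size belongs to a contrast as well as to an outcome. The value 1.19 describes how ictal power differs between two stimulus intensities. In this trial stimulus intensity is not a randomized factor: both arms have a threshold-finding first session and supra-threshold treatment afterwards. What differs by design is the induction agent, and the documents neither give a figure for its effect on ictal power nor argue that it matches the dosing effect.

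What is at stake is how Hypothesis 1.1 will be read. If the trial is described as adequately powered and the comparison is not significant, a reader may take that as evidence that the agents do not differ, although only a very large difference was likely to be detected. The power statement also has some operational weight, because Section 14 gives insufficient power as the reason for terminating the study if more than half of patients refuse the EEG cap.

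**Working it through.** **Inputs from the documents.** d = 1.19, power 0.80, two-sided alpha 0.05, 11 per group, 15% attrition, 26 recruited and 22 analysed (Section 5); t-test for ictal power (Section 13). Section 13's sentence on the t-tests is loosely worded. I read it as a two-sample comparison between arms, as Hypothesis 1.1 requires.

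**Step 1. Reproduce the stated figure (normal approximation).**

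n per group = 2(1.960 + 0.842)² / d² = 15.70 / 1.416 = 11.1.

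This gives the stated 11 if rounded down and 12 if rounded up. Power at 11 per group is Φ(1.19 × √(11/2) − 1.960) = Φ(2.791 − 1.960) = Φ(0.831) = 79.7%. Attrition: 22 / 0.85 = 25.9, so 26, which agrees. Section 5 is therefore broadly reproducible from its own inputs.

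**Step 2. Same inputs, with the t-test that Section 13 names.** Noncentral t, 20 degrees of freedom, noncentrality 1.19 × √5.5 = 2.791.

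- Power at 11 per group: 75.6%.
- Required n per group: 12.1, so 13. Power is 79.6% at 12 and 82.9% at 13.
- Smallest d with 80% power at 11 per group: 1.256, or about 1.26.

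**Step 3. Sensitivity to the agent effect.** The documents give no ketamine v methohexital value, so the values of d below 1.19 are my assumptions (11 per group, two-sided 0.05, t-test).

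| d | Status | Power |
|---|---|---|
| 1.26 | detectable effect | 80% |
| 1.19 | Section 5 proxy | 76% |
| 1.0 | assumed | 61% |
| 0.8 | assumed | 43% |

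**Step 4. Hypothesis 1.2, chi-square.** A standardized mean difference does not fix the power of a comparison of proportions. Suppose one yes/no result per patient, 11 analysed per arm, and no waves on ketamine (0/11). All three are assumptions about how the test would be run.

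- Pearson: the smallest significant methohexital count is 4/11 (p = 0.027). For X ~ Binomial(11, π), P(X ≥ 4) reaches 80% at π of about 45%.
- Fisher: the smallest significant count is 5/11 (p = 0.035). P(X ≥ 5) reaches 80% at π of about 54%.

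**The case against.** Several points on the other side have force.

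- **The source is disclosed.** Section 5 says plainly that the effect comes from a threshold v suprathreshold comparison. This stands: what is missing is a reason for using it as a stand-in.
- **The proxy is not arbitrary.** The outcome is ictal power in both cases, and Section 1 describes ketamine as lowering seizure threshold with longer, more pronounced seizures, and methohexital as shortening seizures and raising threshold. This supports the direction of the hypothesis but gives no magnitude.
- **It is a pilot.** Section 1 says so, and a pilot need not be powered. That lessens the consequence, but Section 5 nevertheless makes a power claim, and that claim should be correct.
- **Section 13 claims no power for Hypothesis 1.2.** A reader might infer that the trial asserts 80% power for the chi-square test. It says only that the effect size will serve as a guide, and d could inform the planned t-tests on wave power. The point that stands is narrower: d cannot be the basis for the chi-square comparison. The unit of that test (waves, sessions or patients) is also undefined, so the 45% and 54% rates hold only under the stated reading.
- **No no-difference conclusion is planned.** This is also true. The misreading of a non-significant result is a risk to guard against, not something the plan commits to.

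**Conclusion.** The concern holds in two separate parts.

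First, the claim of adequate power for Hypothesis 1.1 is unsupported, because d = 1.19 is a stimulus-dose effect used without justification for an agent effect. A reader might go further and infer that the trial is underpowered. The documents do not support that: they do not show that the true agent effect is below 1.19, and it could be larger. The 61% and 43% figures show sensitivity to assumed values only.

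Second, wherever d came from, 80% power is not delivered at d = 1.19 by the named test. With 11 per group the two-sided t-test has about 76%. The shortfall comes from the normal approximation and from rounding 11.1 down, not from the choice of source study. It rests on 11 analysed per arm and a two-sample t-test between arms.

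Both parts concern a stated property of the design and can be corrected in the text.

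**What to change.** Keep 26 recruited and 22 analysed, and make these wording changes.

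1. **Section 5.** Replace the power statement with the detectable effect: with 11 per group, a two-sided t-test at 0.05 has 80% power for d of about 1.26 and about 76% at 1.19; for values labelled as assumed, 61% at 1.0 and 43% at 0.8. Add that 1.19 is a proxy from a stimulus-dose contrast with no agent-specific estimate behind it.
2. **Section 13, Hypothesis 1.1.** Commit to reporting the between-arm difference with a confidence interval, and state that a non-significant result will not be read as no difference.
3. **Section 13, Hypothesis 1.2.** Remove d as the basis for the chi-square comparison. If a detectable rate is given instead, define the unit first and label the figure as assuming one binary result per patient, 11 per arm and no waves on ketamine (about 45% by Pearson, 54% by Fisher).

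The cost is a less favourable stated figure. No extra patients are needed, and arms, endpoints and tests are unchanged. The revised text would still concern ictal power only; it does not supply a power basis for change in depression rating, the primary endpoint in Section 7.

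### Section 5 claims 80% power with 11 patients per group at d = 1.19, but a two-sided two-sample t-test between the arms has about 76%

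*Combined protocol and SAP*

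**What the plan says.** Section 5 bases the sample size on a published comparison of ictal power between a threshold and a suprathreshold group, with d = 1.19 and variances of .24 and .25. It concludes: "Assuming a power of .8 and a two-sided alpha (.05), we will need 11 patients in each group to adequately power our analysis". It adds that this number is one "which is in line with our recruitment projections". The 26 patients to be recruited are said to be a total that "allows for a conservative 15% attrition rate leaving a final sample size of 22". No test, formula or software is named.

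Section 13 links the calculation to one hypothesis: "See effect size calculation in question #5 for hypothesis 1.1". That hypothesis, in Section 1 (Objectives), reads: "Ketamine will be associated with increased ictal power and increased post-ictal suppression compared to methohexital". Section 3 (Study Design) says that "subjects will be randomized to ketamine or methohexitol induction". For the analysis, Section 13 plans "t-tests to compare power of infra-slow waves and total ictal power of seizures and post-ictal suppression in the methohexitol group". For infra-slow waves, where it reports no earlier human data beyond the group's own, it says: "We will use the effect size for hypothesis 1.1 to guide us".

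**The concern.** Eleven per group is a small number for which to claim 80% power in a two-sided t-test, even at d = 1.19. With only 20 degrees of freedom the t critical value is clearly above 1.96, so a sample size from the normal formula falls short by a visible amount. If the planned test is a t-test between arms, the stated power does not belong to the stated sample size.

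This is the only power figure in the document, and Section 5 uses it to call the sample adequate. A reader weighing a null result on hypothesis 1.1 would assume a one-in-five chance of missing an effect of the assumed size, when it is closer to one in four.

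**Working it through.** **Inputs.** From Section 5: d = 1.19; two-sided alpha = .05; power .8; 11 per group; 26 recruited; 15% attrition. The variances, .24 and .25, are nearly equal and have almost no effect on power once d is fixed. The allocation ratio is not stated; 1:1 is taken from the equal group sizes in Section 5.

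**Attrition.** 26 × 0.85 = 22.1, so 22 evaluable. This agrees with the plan.

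**Reproducing the plan's figure (normal approximation).**

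- n per group = 2 × (1.960 + 0.8416)² / 1.19² = 11.09.
- Power at 11 per group = 79.7%.
- Over the rounding range of d, n is 11.18 (d = 1.185) to 10.99 (d = 1.195), and power at 11 is 79.4% to 80.0%.

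The stated 11 is therefore consistent with this formula, with 11.09 rounded down.

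**Power of the two-sample t-test (noncentral t).**

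- Degrees of freedom = 11 + 11 − 2 = 20; critical value 2.086.
- Noncentrality = 1.19 / √(1/11 + 1/11) = 2.79.
- Power = P(|T| > 2.086) = 75.6%.

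A simulation with the stated variances and 11 per group gave 75.7% for the pooled t-test and 75.4% for Welch's, so the choice between them does not matter.

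**Can rounding or allocation recover 80%?** At 11/11, d = 1.185 gives 75.3% and d = 1.195 gives 76.0%. For other group sizes at d = 1.19:

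| Evaluable | Split | Power |
|---|---|---|
| 22 | 11/11 | 75.6% |
| 22 | 12/10 | 75.3% |
| 22 | 13/9 | 74.2% |
| 23 | 12/11 | 77.6% |
| 24 | 12/12 | 79.6% |
| 24 | 13/11 | 79.3% |
| 25 | 13/12 | 81.2% |
| 26 | 13/13 | 82.9% |

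Solving for n gives 12.12 per group, hence 13 evaluable per group for at least 80%.

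**Sensitivity to d at 11/11.** Power is 61% at d = 1.0, 69% at 1.1 and 83% at 1.3. The effect detectable with 80% power is d = 1.256.

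**The case against.** Four points deserve weight.

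- *The 11 is not a slip of arithmetic.* It follows from a standard approximation, and Section 5 names no test. This explains the figure but does not rescue it: Section 13 plans t-tests, and at 20 degrees of freedom the approximation overstates power by about 4 points (79.7% against 75.6%).
- *The test is not fully specified.* The t-test sentence in Section 13 ends by naming only the methohexital group, so a between-arm test has to be inferred. That stands, and the conclusion is conditional on it. It is still the natural reading: a comparison within one arm cannot address hypothesis 1.1, and a paired test does not fit two randomised arms. A one-sided test would have 85.3% power, but Section 5 specifies two-sided.
- *The consequence is small.* This is a pilot, and d is borrowed from a contrast of stimulus levels, not of induction agents. A shortfall of 4.4 points lies well inside the range that uncertainty in d produces. Section 5 also cites recruitment projections, so power is not its only rationale. All of this stands.
- *The full attrition allowance may not be used.* With one loss or none from 26, power exceeds 80%; with two it is 79.6% or 79.3%. That limits the practical effect, but Section 5 attaches .8 to 11 per group, and that statement is what is wrong.

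**Conclusion.** The concern holds. For a two-sided .05 two-sample t-test between arms at d = 1.19, 11 evaluable patients per group give 75.6% power (75.3% to 76.0% over the rounding of d), not 80%; the Type II error is about 24%. The result rests on d = 1.19 as stated, equal allocation, and reading the t-test for hypothesis 1.1 as a comparison of the two randomised arms. The normal-approximation origin of the 11 is an inference. The computation is certain; the link to the planned test is a fair reading of wording that leaves some room. The finding does not extend to the other comparisons, because Section 13 carries over the effect size and not the 80% figure. It is a modest misstatement that should be corrected because the correction is almost free, not because it threatens the trial.

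**What to change.** Keep 26 patients and restate Section 5 along these lines:

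> With 22 evaluable patients (11 per group), a two-sided .05 two-sample t-test between the ketamine and methohexital arms has about 76% power for d = 1.19 and 80% power for d of about 1.26 or larger. At this size, power is 61% for d = 1.0 and 83% for d = 1.3. If all 26 patients are evaluable, power for d = 1.19 is about 83%.

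The test and the method of calculation should be named. If the between-arm reading is what is meant, the t-test sentence in Section 13 should say so too.

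The cost is a few words of text and a slightly less favourable stated power. No patients are added, and conduct and analysis are unchanged. If the sponsor prefers to keep the 80% claim, 13 evaluable per group are needed: 26 / 0.85 = 30.6, so 31 recruited, or 32 for equal arms. For a pilot, restating the power is the proportionate choice.
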